9.3.3. Exposure

Exposure definitions will use the following variables:

- **VKA** will be defined as B01AA ATC code;
- **DOAC** will be defined as B01AF01 ATC code for rivaroxaban and B01AE07 ATC code for dabigatran;
- **DOAC high dosage** will be defined using CIP codes for rivaroxaban 20mg and dabigatran 150mg;
- **DOAC low dosage** will be defined using CIP codes for rivaroxaban 15mg and dabigatran 110mg;
- **Treatment group** will be defined by the first anticoagulant dispensation during the inclusion period, i.e. rivaroxaban high or low dosage, dabigatran high or low dosage, or VKA;
- **Index date** will be defined as the date of the first dispensation of the anticoagulant in the treatment group;
- **Duration of a drug dispensation** will be defined as the number of daily doses for DOAC and 30 days for VKA;
- **Drug (DOAC or VKA) exposure** will be defined as the period starting at the index date and ending at the date of the last drug dispensation plus the duration of the last drug dispensation for subject with a drug discontinuation (defined below) or at the date of drug switch (defined below), or at the end of follow-up, whichever is the earliest;
- **Drug (DOAC or VKA) discontinuation** will be defined with a grace period of 60 days for the main analysis and 30 days for a sensitive analysis after the last dispensation plus the duration of the last drug dispensation;
- **Drug (DOAC or VKA) switch** defined as a dispensation of another anticoagulant, including heparin and LMWH dispensation (B01AB ATC code), for subject with a drug discontinuation;
- **Post drug (DOAC or VKA) exposure** will be defined as the period starting at date of the end of drug exposure (see above) and ending at the date a new prescription of an anticoagulant or at the end of follow-up, whichever is the earliest;
- **DOAC compliance** will be estimated using Medication Possession Ratio (MPR) during drug exposure defined by the number of defined daily doses dispensed, divided by the number of days of drug exposure for DOAC. Considering the variable dosage of VKA between subjects and over time in individual subjects, no defined daily dose can be defined, and therefore no MPR for VKA exposure.
- During a hospitalisation, drugs are provided by the hospital, and this time will be taken into account for calculation of drug exposure and drug discontinuation.

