9.3.5. Potential confounding

The potential confounders considered will be:

- **Gender and age** at index date;
- **CHA₂DS₂-VASc score** (Lip GY 2010) at index date, modified to take into account the availability of information in the database, and defined as the sum of points from following stroke risk factors: congestive heart failure (+1), hypertension (+1), age ≥ 75 years (+2), diabetes mellitus (+1), stroke or transient ischemic attack (TIA) history (+2), vascular disease history (+1), age 65-74 years (+1), female gender (+1), within tree-year database history;
- **CHADS₂ score** (for descriptive analysis, Waterman 2001) at index date, modified to take into account the availability of information in the database, and defined as the sum of points from following stroke risk factors: congestive heart failure (+1), hypertension (+1), age ≥ 75 years (+1), diabetes mellitus (+1), stroke or transient ischemic attack history (+2);
- **HAS-BLED score** (Pisters 2010, Lip GY 2011), modified to take into account the availability of information in the database, and defined as the sum of points from bleeding risk factors: hypertension (+1), abnormal renal function (+1), abnormal liver function (+1), stroke history (+1), bleeding history (+1), age > 65 years (+1), drug predisposing to bleeding (+1), within tree-year database history;

- **High dimensional Propensity Scores (hdPS)**: the probability to be treated by one of the studied drugs (rivaroxaban versus VKA, rivaroxaban versus dabigatran), will be estimated using hdPS taking into account all information of the database, with multiple data dimensions from subjects and disease characteristics, other LTD, other comorbidities using one-year history of hospitalisation (primary, linked, or associated diagnosis), three-year history of number of systemic drugs dispensed by therapeutic class (ATC 3 digit, including antacids A02A and drugs for peptic ulcer A02B) and of healthcare reimbursements (number of GP visits, specialist visits, emergency room visits, days of hospitalisation, nurse care and lab tests).
- **Drug predisposing to bleeding** during drug exposure: ASA, NSAIDs, antiplatelet agent and heparin or LMWH.

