9.7.1. Outcomes

Outcomes will be analysed using survival methods for the first occurrence of each outcome:

- Estimation of the one-year and two-year cumulative incidence of each outcome, and according to individual diagnose of each outcome, during drug exposure for rivaroxaban, dabigatran, and VKA, using Kaplan-Meier estimate for death and cumulative incidence function for clinical outcomes, in order to take into account death as a competing risk.
- Estimation of the incidence rate (per 100 PY exposed) of each outcome, and according to individual diagnose of each outcome, during drug exposure or if the risk is not constant over the time, during periods with a constant risk.
- Comparison of the one-year and two-year risk of each outcome during drug exposure, rivaroxaban versus VKA, and rivaroxaban versus dabigatran, using Cox proportional hazard risk model (Cox 1972) for death and Fine and Gray model (Fine 1999) for clinical outcomes, in order to take into account death as a competing risk. Hazard ratio will presented as a point estimate with its 95% confidence interval.
 - Main analysis will compare the incidence of each outcome for matched subjects with time dependant variables adjustment for drug predisposing to bleeding during drug exposure (time dependant variable),
 - Secondary analysis will compare the incidence of each outcome with all subjects, except outliers, with adjustment for hdPS and drug predisposing to bleeding during drug exposure (time dependant variable) for the rivaroxaban versus VKA comparison; and plus low or high DOAC dosage at index date for the rivaroxaban versus dabigatran comparison.
 - Prognostic analysis will be done with all subjects, but outliers, to assess outcome risk factors, including gender, age, CHA₂DS₂-VASc and HAS-BLED scores, low or high dosage at index date for DOAC, drug predisposing to bleeding during drug exposure (time dependant variable) and significant baseline characteristics. The significant baseline characteristics will be identified firstly with univariate analyses, and therefore using a forward stepwise (taking into account the size of the database, the p threshold will be set at 1/1000 for variables selection and at 5% for the stepwise procedure).

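### The main matched model adjusts every outcome for co-medication dispensed after the index date, and no planned analysis leaves that adjustment out

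*Protocol*

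**What the plan says.** Section 9.7.1 Outcomes, and the abstract in the same sense, fixes the model: the main comparison of each outcome is made "for matched subjects with time dependant variables adjustment for drug predisposing to bleeding during drug exposure". Clinical outcomes use the "Fine and Gray model (Fine 1999) for clinical outcomes, in order to take into account death as a competing risk"; mortality is compared "using Cox proportional hazard risk model (Cox 1972) for death".

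Section 9.3.5 lists the adjusted variable among the potential confounders and defines it as "ASA, NSAIDs, antiplatelet agent and heparin or LMWH" during drug exposure. Section 9.3.3 starts drug exposure at the index date, so the variable is measured after the treatment group is set.

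The baseline counterpart is already used. The modified HAS-BLED score in section 9.3.5 gives a point for predisposing drugs in the three-year history. The hdPS includes HAS-BLED (section 9.7.3) and three-year dispensing counts by therapeutic class (section 9.3.5).

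The secondary analysis in all subjects repeats the time-dependent adjustment. The sensitivity analyses in section 9.7.1 Generalities vary the grace period, the AF definition and the classification of unspecified events. None removes the covariate.

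**The concern.** Something that arises after the index date cannot confound the choice made on that date, but it can lie on the path from that choice to the outcome. A patient or prescriber may use fewer or more NSAIDs or antiplatelets because of the anticoagulant, or because of an intermediate event. For example, an acute coronary syndrome during exposure does not end follow-up for bleeding, so the antiplatelet that follows it becomes a covariate in the bleeding model.

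Two things follow if treatment affects co-drug use. First, the adjusted hazard ratio excludes whatever part of the on-treatment effect runs through co-medication. Second, co-drug use then depends on both treatment and patient frailty, so conditioning on it ties treatment to frailty within co-drug strata. This is collider bias, and matching at baseline does not prevent it.

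A separate difficulty affects the clinical outcomes. Fine and Gray keeps subjects who died in the risk set. Dispensing is an internal covariate with no value after death, and the protocol states no convention for it. The adjusted subdistribution hazard ratio then loses its direct link to cumulative incidence, which is the usual reason for choosing that model.

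**Working it through.** The protocol states no figure on this point, so there is none to reproduce. The check is a simulation of a bleeding outcome, for illustration only.

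**Inputs from the protocol (section 9.5):** clinically relevant bleeding 2.6 per 100 PY and death 3.5 per 100 PY. Follow-up is two years (section 9.1).

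**Assumptions not in the documents:** co-drug starts at 20 per 100 PY in both arms in run (a), and at 15 (rivaroxaban) versus 30 (comparator) per 100 PY in runs (b) to (d); a co-drug hazard ratio of 2 for bleeding and for death; a direct treatment hazard ratio of 0.85, or 1.00 in run (d); a shared log-normal frailty with SD 0 or 0.7.

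**Method:** 1,000,000 subjects per arm and 48 intervals. The subdistribution model was approximated by an interval Poisson fit that keeps subjects who died at risk. The adjusted model was fitted twice: once carrying the last covariate value forward after death, once setting it to 0.

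| Run | Direct HR put in | Treatment-only HR | Adjusted, carried forward | Adjusted, 0 after death | Co-drug HR under the two conventions |
|---|---|---|---|---|---|
| (a) no effect on co-drug starts, no frailty | 0.85 | 0.845 | 0.845 | 0.845 | 2.005 / 2.123 |
| (b) starts halved, no frailty | 0.85 | 0.773 | 0.845 | 0.849 | 1.997 / 2.119 |
| (c) starts halved, frailty SD 0.7 | 0.85 | 0.780 | 0.916 | 0.920 | 3.229 / 3.474 |
| (d) as (c), no direct effect | 1.00 | 0.900 | 1.060 | 1.066 | 3.261 / 3.506 |

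**Hand check of run (b), ignoring deaths.** With start rate r over T = 2 years, the average share of time on the co-drug is 1 − (1 − e^(−rT))/(rT).
- r = 0.15: 1 − 0.2592/0.3 = 0.136.
- r = 0.30: 1 − 0.4512/0.6 = 0.248.
- With a co-drug hazard ratio of 2, the mean rates scale by 1.136 and 1.248, so the treatment-only ratio is 0.85 × 1.136/1.248 = 0.774. The simulation gave 0.773.

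**Reading the results**
- Run (a): the adjustment changes nothing.
- Run (b): the adjusted ratio returns the direct effect and drops the mediated part (0.845/0.773 = 1.09).
- Runs (c) and (d): the adjusted ratio is neither the on-treatment effect nor the direct effect. In (d) the treatment-only value is 0.90, the direct effect is 1.00 and the adjusted value is 1.06. The excess over 1.00 is collider bias.
- The convention after death moved the treatment ratio by at most 0.006 (1.060 to 1.066), but the co-drug ratio by about 6 to 8% (2.123/2.005 = 1.06; 3.474/3.229 = 1.08).

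**Milder assumptions.** A separate simulation had no direct effect and no competing death. It assumed two weeks of heparin overlap in 30% of VKA and 5% of rivaroxaban starters, with a hazard ratio of 3, and gave 0.982 unadjusted and 1.000 adjusted. With frailty and one-third fewer later co-drug starts added, it gave 0.938 and 1.004. These are shifts of 2 to 6%.

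**The case against.** The best defence is that every size above is assumed. The documents do not show that anticoagulant choice changes co-drug use, and without such an effect the shift is nil. Heparin overlap at VKA initiation, moreover, has no stated counterpart for rivaroxaban versus dabigatran, which is half of the main objective. Section 9.7.6 will also report co-dispensation by group in matched subjects, with standardised differences, so an imbalance would be visible. All of this stands, and it limits what can be said about impact. It does not give a reason for the adjustment: seeing an imbalance does not produce an estimate free of it, and none is planned.

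Four stronger readings are tempting, and the documents do not support them.

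- *The result would miss the total effect of starting rivaroxaban.* Section 8 targets risk during drug exposure, and section 9.3.3 ends exposure at discontinuation or switch. What is lost is part of the on-treatment effect. Dropping the covariate would not yield an effect of initiation regardless of later treatment.
- *Heparin/LMWH has two conflicting roles.* Section 9.3.3 does define a switch as "including heparin and LMWH dispensation (B01AB ATC code"), but limits this to subjects who have discontinued the index drug. Heparin given alongside the index drug is co-medication. On paper the roles are separate.
- *A shift of 2 to 6% matches the precision of the study.* With 20,000 per arm, one year and 2.6 per 100 PY, there are 20,000 × 0.026 = 520 events per arm. The half-width on the log scale is 1.96 × √(2/520) = 0.12, so about 12%. The milder shifts fall well inside sampling error.
- *The Fine and Gray problem distorts all results.* It does not apply to death. It barely moved the treatment ratio, and the reported cumulative incidences come from the cumulative incidence function, not from this model.

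**Conclusion.** Wrong as written. The protocol conditions its main matched hazard ratios for stroke/SE, major bleeding and death on a post-index variable that treatment can influence. Baseline use is already in the matching, and no analysis without the adjustment is planned. If treatment affects co-drug use, the headline estimate excludes part of the on-treatment effect and may be biased further through shared frailty.

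The size cannot be fixed from the documents. It ranged from nil (no treatment effect on co-drug use), through 2 to 6% under mild assumptions, to 9 to 18% when treatment halved co-drug starts (0.845/0.773 = 1.09; 1.060/0.900 = 1.18). These runs concern a bleeding outcome; for death only the post-treatment conditioning applies, and its size was not simulated.

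For stroke/SE, major bleeding, CRB and ACS, the undefined covariate after death is a further fault of definition. Its practical effect on the treatment hazard ratio was negligible in simulation.

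**What to change.** In section 9.7.1 Outcomes and the abstract, define the main analysis as the matched comparison with treatment only, allowing baseline covariates if wanted. Keep the time-dependent co-drug adjustment as a sensitivity analysis, fitted as a cause-specific Cox model instead of Fine and Gray, and state that it does not estimate the full on-treatment effect. Move the during-exposure variable out of the list of potential confounders in section 9.3.5; its baseline form stays in HAS-BLED and the hdPS.

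The cost is a protocol wording change before analysis. Because the model is fixed in the protocol, a change in the SAP alone would leave the two documents in conflict. No new data are needed, and the adjusted result is still reported.

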In France, Xarelto[®] and Pradaxa[®] were launched in this indication in August 2012, and Eliquis[®] in January 2014. The Transparency Committee of the *Haute Autorité de Santé* (HAS) gave a positive opinion for the reimbursement in this indication with a substantial medical benefit (SMR important) but no improvement in existing benefit (ASMR V), no expected public health impact, and a target population of 500 000 patients. As part of this procedure, the Transparency Committee requested Bayer to provide additional data documenting the therapeutic benefit of Xarelto[®] under actual conditions of use compared with the normal treatment of at-risk patients with NVAf:

- The characteristics of the treated patients, in particular age, gender, history and cardiovascular risk factors,
- The conditions of use of Xarelto[®]: reasons for starting treatment (particularly, first-line or second-line prescription, and risk factors associated with AF), any previous anticoagulant treatment and level of control thus obtained, concomitant treatments (in particular, antiplatelet agents and medicines with a risk of interaction), prescribed dosage (dose, amount administered daily and duration of prescription), frequency and reasons for any discontinuation of treatment and treatments started as a back-up,
- The impact on morbidity and mortality (events avoided and adverse effects, particularly bleeding), treatment compliance and quality of life in the medium and long term.

ANSM,¹ the French medicines agency, commissioned two studies using the French national claims and hospital database:

- The NACORA-BR study, performed by the CNAMTS,² was a cohort study with a main objective to compare the short-term risk of major bleeding for new NOAC users naive of VKA during the second half of 2012 to new users of VKA during the second half of 2011. Secondary objectives were to compare the risk of arterial events (stroke, systemic embolism), the risk of myocardial infarction (MI) over the same period in patients starting treatment within the AF indication, and the 30-day survival for patients hospitalized for major bleeding. This study concluded to no significant statistical difference between NOACs, dabigatran or rivaroxaban, and VKAs for the short-term risk of bleeding or arterial thromboembolic short-term risk during the early phase of anticoagulant therapy in NVAF patients (CNAMTS 2014, Maura 2015).

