- The NACORA-Switch study, led by the ANSM, was a cohort study with the same main and secondary objectives for patients who switched from VKA to NOAC compared to matched patients who remained on VKA. The authors concluded that the short-term risk of severe bleeding, stroke and systemic embolism, myocardial infarction was not increased for patients switching from VKA to DOAC compared to those remaining on VKA (ANSM 2014).

The two study underline that they were conducted at the early phase of dabigatran and rivaroxaban marketing for SPAF with a short-term follow-up (3 months). The early period of marketing of a new drug is generally considered as a learning period during which disease severity and history, drug prescription and utilisation do not necessary reflect the use of the drug in daily practice some months later.

In order to provide additional information to answer the HAS requests, especially the impact on morbidity and mortality, with a longer follow-up than for the NACORA studies, a rivaroxaban versus VKA comparison, as well as a face to face comparison between the two DOAC (rivaroxaban versus dabigatran). Bayer committed to a cohort study to be initiated about six months after the launch of the two first DOAC for SPAF with two years of follow-up, using the French national claims and hospital database.

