9.7.3. Propensity score

The probability to be treated by rivaroxaban or VKA, as well as rivaroxaban or dabigatran will be estimated with hdPS at index date (Schneeweiss 2009, Rassen 2012). The hdPS will be estimated using a logistic regression model with a large set of variables at index date and three-year history before inclusion, including gender, age, CHA₂DS₂-VASc and HAS-BLED scores. The subjects without correspondence between both hdPS distributions will be considered as outliers (two extremities of the hdPS distribution).

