9.7.4. Matching

For the rivaroxaban versus VKA comparison, subjects will be matched 1:1 on hdPS and index date within each population (specific and sensitive); For the rivaroxaban versus dabigatran comparison, subjects will be matched 1:1 on high or low DOAC dosage at index date, hdPS and index date within each population (specific and sensitive). The matching will use the logit of the hdPS with calipers of width equal to 0.2 of the standard deviation of the logit of the hdPS (Austin 2011).

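### The all-subject adjusted models omit index date, a matching factor in the main analysis, and so leave the secondary results open to residual calendar-time confounding

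*Protocol*

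**What the plan says.** Protocol section 9.7.4 (Matching) sets the main analysis. For rivaroxaban versus VKA, "subjects will be matched 1:1 on hdPS and index date within each population (specific and sensitive" cohorts. For rivaroxaban versus dabigatran, "subjects will be matched 1:1 on high or low DOAC dosage at index date, hdPS and index date within each population".

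The second section numbered 9.7.1 (Outcomes) sets the secondary analysis of all subjects except outliers. The model is fitted "with adjustment for hdPS and drug predisposing to bleeding during drug exposure (time dependant variable) for the rivaroxaban versus VKA comparison". The other comparison keeps those terms and gains a single further one: "and plus low or high DOAC dosage at index date for the rivaroxaban versus dabigatran comparison". The abstract gives the same two sets.

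The hdPS is described in two places. Section 9.7.3 builds it "with a large set of variables at index date and three-year history before inclusion", including gender, age and the two risk scores. Section 9.3.5 says that the probability of treatment "will be estimated using hdPS taking into account all information of the database", and then names patient and disease characteristics, long-term disease registrations, comorbidities, drug classes and resource use. Neither place names the calendar date.

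Section 9.7.1 (Generalities) repeats the sensitivity analyses both in the matched cohorts and with statistical adjustment in all subjects.

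**The concern.** The protocol treats index date as something to control separately from the hdPS, and does so in the design of its main analysis. The adjusted model in all subjects then carries over one of the extra matching factors (dosage) but not the other (index date), and no reason is given. Because the adjustment set is written out explicitly, this is a stated choice rather than a detail left open.

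Inclusion runs over two calendar years, and the market changed within them. Rivaroxaban and dabigatran were launched in this indication in August 2012, "and Eliquis[®] in January 2014", at the midpoint of inclusion. If the balance between treatments shifts over 2013-2014, and outcome risk also changes with calendar time in a way that the hdPS does not capture, the adjusted hazard ratio absorbs part of that trend. The omission applies to both comparisons, and it is carried into each sensitivity analysis repeated with adjustment.

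**Working it through.** **Step 1: compare the control sets.**

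| Factor | Matched, vs VKA | Adjusted, vs VKA | Matched, vs dabigatran | Adjusted, vs dabigatran |
|---|---|---|---|---|
| hdPS | yes | yes | yes | yes |
| Index date | yes | **no** | yes | **no** |
| Dosage | not applicable | not applicable | yes | yes |
| Time-dependent bleeding drugs | yes (in model) | yes | yes (in model) | yes |

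Index date is the only factor lost between the two analyses.

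**Step 2: does the hdPS cover it?** Not by name. Variables at index date are covariates measured on that day, not the date itself. Matching on index date alongside the hdPS suggests that the score was not meant to carry it. The wording of 9.3.5 is broad enough that inclusion cannot be ruled out.

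**Step 3: scale.** The protocol gives no figure to reproduce, neither starter shares by year nor outcome trends, so every input here is an assumption. Let a and b be the shares of rivaroxaban and dabigatran starters indexed in 2013, and h the 2014:2013 outcome hazard ratio that remains after hdPS adjustment. With no true treatment effect, the model that ignores index date gives approximately

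spurious HR = [a + (1 − a)h] / [b + (1 − b)h].

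| a | b | h = 0.80 | h = 1.25 |
|---|---|---|---|
| 0.50 | 0.55 | 0.900/0.910 = 0.989 | 1.125/1.1125 = 1.011 |
| 0.45 | 0.60 | 0.890/0.920 = 0.967 | 1.1375/1.100 = 1.034 |
| 0.40 | 0.65 | 0.880/0.930 = 0.946 | 1.150/1.0875 = 1.057 |

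If h = 1, or if a = b, the ratio is exactly 1.

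The formula also applies to rivaroxaban versus VKA, for which the protocol gives no shares either. As generic pairs at h = 0.80, 2013 shares of 55% and 45% give 0.910/0.890 = 1.022, 60% and 40% give 0.920/0.880 = 1.045, and 70% and 30% give 0.940/0.860 = 1.093. The last is a large imbalance, shown only to mark how the result depends on the shares.

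**Step 4: set against the study's precision.** The table in section 9.5, drawn up for matched subjects, lists 1.12 as its smallest hazard ratio above 1 (5% incidence, 20 000 per group) and 1.20 at 2% incidence with the same group size. On the log scale, ln(1.057) = 0.055, against ln(1.12) = 0.113 and ln(1.20) = 0.182. The extreme corner of the dabigatran grid is therefore about half of the first and under a third of the second.

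**The case against.** The best case for the protocol has four parts.

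First, the list of hdPS inputs is open, and the SAP may place calendar time in the score or the model. This stands as far as the hdPS goes, and one sentence would settle it. It does not reach the outcome model, whose adjustment set is written out and omits index date.

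Second, a shift in drug mix alone does not confound. Outcome risk must also change with calendar time after adjustment, and the hdPS already covers age, sex, both risk scores, comorbidities and three years of drug and resource use. This stands. It is why h above has to be a residual hazard ratio, and why the range of 0.80 to 1.25 is generous.

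Third, a reader might take the remark in section 7 about "a learning period during which disease severity and history, drug prescription and utilisation do not necessary reflect the use of the drug" as the protocol's own admission of drift during inclusion. It is not. The remark criticises the earlier three-month studies run at launch, and the next paragraph answers it by starting this cohort about six months later. The documents do not say that case mix or prescribing drifts within 2013-2014.

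Fourth, a reader might treat the all-subject analysis as the planned check on the matched result, so that any disagreement becomes unreadable. Section 9.7.1 (Generalities) calls it only a secondary analysis, and section 9.9 states a robustness purpose for the sensitive NVAF definition alone. The two analyses also differ in population, so a disagreement would have more than one explanation even with index date included.

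**Conclusion.** The point holds as an inconsistency between the matching set and the adjustment set, present in the abstract and the body and in both comparisons. It leaves the secondary all-subject hazard ratios, and the sensitivity analyses repeated with adjustment, open to residual calendar-time confounding. That bias actually occurs is not shown. It needs both different index-date distributions between treatments and an outcome trend beyond what the hdPS captures, and the protocol documents neither.

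Under the assumed rivaroxaban and dabigatran shares, with a residual 2014:2013 hazard ratio of 0.80 to 1.25, the spurious hazard ratio is about 0.95 to 1.06 at the extreme and 0.99 to 1.01 when the shares are close. No specific figure can be given for the VKA comparison. The effect is probably small. The primary matched result controls index date by design, and nothing here counts against it.

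**What to change.** In the all-subject models for both comparisons, add calendar quarter of index date (eight quarters over 2013-2014) as a stratum of the baseline hazard or as a covariate. Do the same in every sensitivity analysis that uses statistical adjustment. Changing the hdPS models as well is not needed. If calendar date is in fact already meant to enter the hdPS, say so in one sentence.

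The cost is one variable already held in the data, at most seven extra parameters in a cohort expected to number about 100 000, and a line of wording in the protocol or SAP. No new extraction is required, and the matched analysis does not change.

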8. RESEARCH QUESTION AND OBJECTIVES

The research question is to assess the one-year and two-year benefit-risk of rivaroxaban for SPAF compared to VKA and dabigatran among new anticoagulant users.

The main study objective is to compare the one-year and two-year risk of each of the following individual outcomes: Stroke and systemic embolism (SE), major bleeding and death between new users of anticoagulant for SPAF during drug exposure: rivaroxaban versus VKA, and rivaroxaban versus dabigatran.

Secondary objectives are:

- To describe the drug exposure to rivaroxaban, dabigatran, and VKA for SPAF in new users, as well as pattern of use;

¹ Agence Nationale de Sécurité du Médicament et des produits de santé (French Medicines Agency)

² Caisse Nationale de l'Assurance Maladie des Travailleurs Salariés (French National Health Insurance Fund for Salaried Workers)

- To compare the one-year and two-year risk of the following individual outcomes: a composite of stroke and SE, major bleeding and death, clinically relevant bleeding (CRB) and acute coronary syndrome (ACS) between new users of anticoagulant for SPAF during drug exposure: rivaroxaban versus VKA, and rivaroxaban versus dabigatran;
- To estimate the cumulative incidence and the incidence rate of each individual main and secondary outcome (stroke and SE, major bleeding, CRB, death, composite criteria, and ACS), as well as according individual diagnose of each of these outcomes, during drug exposure for rivaroxaban, dabigatran, and VKA;
- To estimate the cumulative incidence of each individual main and secondary outcome (stroke and SE, major bleeding, CRB, death, composite criteria, and ACS), as well as according individual diagnose of each of these outcomes during post-anticoagulant exposure for rivaroxaban, dabigatran, and VKA (i.e. after anticoagulant discontinuation);
- To assess outcome risk factors, including (but not limited to), gender, age, stroke and bleeding risk scores (CHA₂DS₂-VASc and HAS-BLED), low or high dosage at index date for DOAC, drug predisposing to bleeding during drug exposure and significant baseline characteristics;
- To describe and compare healthcare resources utilisation related to SPAF during rivaroxaban, dabigatran, and VKA exposure, including outcomes, and their related costs from the societal perspective and from the French healthcare insurance perspective.

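### The prognostic analysis lists age and sex beside full risk scores that already award points for them, so in a joint model their hazard ratios would be shifted and would not answer the risk-factor objective

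*Protocol*

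**What the plan says.** Section 8 makes the identification of risk factors a secondary objective: "To assess outcome risk factors, including (but not limited to), gender, age, stroke and bleeding risk scores". Section 9.7.1 (Outcomes) implements it: "Prognostic analysis will be done with all subjects, but outliers, to assess outcome risk factors, including gender, age". The list continues with the full CHA2DS2-VASc and HAS-BLED scores, the DOAC dose level at index, time-dependent drugs that promote bleeding and baseline characteristics found significant. Those characteristics come from a univariate screen and then forward stepwise selection: "the p threshold will be set at 1/1000 for variables selection and at 5% for the stepwise procedure". The data-analysis part of the abstract repeats the list.

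Section 9.3.5 defines the scores. CHA2DS2-VASc includes "age ≥ 75 years (+2), diabetes mellitus (+1") and then "age 65-74 years (+1), female gender (+1), within tree-year database history". HAS-BLED includes "age > 65 years (+1), drug predisposing to bleeding (+1), within tree-year database history" and has no sex item. Hypertension and stroke history appear in both scores.

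The protocol does not say that the scores enter without their age and sex points, that scores and components go into separate models, or how the overlap would be read.

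**The concern.** A list of named covariates followed by forward stepwise selection reads most naturally as one multivariable model. In such a model the sex coefficient is conditional on a total that already holds a point for being female. The age coefficient is conditional on two totals that already hold points for age. Neither coefficient then says whether, or how strongly, sex or age predicts the outcome, although both are the first factors named in the objective.

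An HR for female sex near or below 1 could be read as showing that sex is neutral or protective when it is not, and the effect of age would look weaker than it is. Section 9.5 expects about 100,000 subjects in the specific cohort. A large sample narrows the confidence interval around the shifted value but does not remove the shift. The same applies to any score component, such as hypertension or stroke history, that stepwise selection brings in as a baseline characteristic.

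**Working it through.** The protocol gives no figure on this point, so there is none to reproduce.

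**1. Overlap by definition (section 9.3.5)**

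| Item | CHA2DS2-VASc | HAS-BLED |
|---|---|---|
| Female sex | +1 | none |
| Age | +1 at 65-74, +2 at 75 and over | +1 above 65 |
| Hypertension | +1 | +1 |
| Stroke history | +2 (stroke or TIA) | +1 |

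**2. Algebra for sex**

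Let b be the true log-HR for female sex and write the score as S = female + age points + the rest. A model with female (coefficient g) and S (coefficient c per point) gives women a total of g + c. If that total matches the truth, g = b − c, so

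reported sex HR ≈ true sex HR / HR per point.

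The shift is downward whenever the per-point HR exceeds 1. The argument needs only a log-linear model, so it applies to the Cox and the Fine and Gray models alike. The protocol gives no sex HR or per-point HR, so both are assumed here and shown over a range:

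| HR per point | True sex HR 1.0 | True sex HR 1.2 |
|---|---|---|
| 1.1 | 1/1.1 = 0.91 | 1.2/1.1 = 1.09 |
| 1.2 | 1/1.2 = 0.83 | 1.2/1.2 = 1.00 |
| 1.3 | 1/1.3 = 0.77 | 1.2/1.3 = 0.92 |
| 1.4 | 1/1.4 = 0.71 | 1.2/1.4 = 0.86 |

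**3. Simulation with both scores in the model**

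All inputs are assumptions: 400,000 subjects, age mean 74 and SD 11, 48% female, hypertension 60%, heart failure 30%, diabetes 22%, stroke history 12%, exponential event times and a Poisson likelihood with person-time offset. The true age HR per 10 years was set at 1.30 or 1.60.

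| Quantity | True HR | Age + sex + both full scores | Scores without age and sex points, or components instead |
|---|---|---|---|
| Female sex | 1.00 | 0.82 | 1.01-1.03 |
| Female sex | 1.11 | 0.89 | 1.12 |
| Female sex | 1.20 | 0.96-0.97 | 1.20-1.23 |
| Female sex | 1.35 | 1.06-1.07 | 1.34-1.36 |
| Age per 10 years | 1.30 | 1.11-1.14 | 1.28-1.31 |
| Age per 10 years | 1.60 | 1.41-1.44 | 1.59-1.63 |

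The fitted CHA2DS2-VASc HR was 1.24-1.27 per point. The algebra agrees: 1.00/1.24 = 0.81 against 0.82 fitted, and 1.35/1.27 = 1.06 against 1.06-1.07.

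**4. Can the model be fitted?**

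Yes, with continuous age: it is full rank and the variance inflation factors run from 1.2 to 2.4. It becomes singular (rank 9 of 10 columns) only if age enters in the CHA2DS2-VASc bands and all the other components of that score enter as well.

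**The case against.** The strongest reply is that joint entry is inferred. The text lists factors to be assessed and does not say that they share one model; the stepwise sentence concerns the baseline characteristics; and section 9.7 defers to a statistical analysis plan. That plan could separate the models. This stands as a limit on the claim, but it does not dispose of it. The protocol itself names the overlapping covariates side by side, in the objective and in the method, without a separation rule, so a plan that follows it as written inherits the overlap.

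A second reply is that the coefficients are legitimate conditional estimates which show where the score's fixed weights fit badly. That is true, and can be of interest, but it is not the stated objective.

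A reader might infer four stronger things that the documents and the check do not support:

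- **Both scores contain sex.** HAS-BLED as defined has no sex item, so the sex overlap comes from CHA2DS2-VASc alone.
- **The age and sex HRs are mere artefacts.** The model is estimable and the collinearity moderate. In the simulation age stayed above 1, attenuated and not neutral or reversed, and so did a sex effect of 1.35.
- **Drugs that promote bleeding are counted twice in the same way.** The HAS-BLED item is measured at index from history. The separate covariate is time-dependent use during exposure, which is a different variable.
- **The rivaroxaban comparisons are affected.** They do not use this model.

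**Conclusion.** The point holds for the prognostic analysis, on the natural reading that the listed variables enter one model. The sex HR would be shifted downward by about the CHA2DS2-VASc per-point HR and may change direction; the age HR would be attenuated. The direction for sex follows from the score definition whenever the per-point HR exceeds 1. The sizes, including the reported range of 1.09 to 0.86 for a true sex HR of 1.2 and the fall in the age HR from 1.30 to 1.11-1.14, rest on assumed effects and, for the simulation, assumed prevalences. They are illustrations, not predictions for this cohort. Importance is low: one secondary objective is affected, and the matched and hdPS-adjusted comparisons are not.

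**What to change.** In section 9.7.1 (Outcomes) and the matching paragraph of the abstract, state that scores and components are fitted in separate prognostic models for each outcome: one with the risk scores and without their components, the other with age, gender and the individual components and without the scores. Alternatively, state that the scores are stripped of their age and sex points in any model from which age and sex HRs are reported. In the simulation either form returned HRs close to the true values. The cost is one extra model per outcome, with no new data and no change to the main or secondary treatment comparisons.
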